6.6 Sham Procedures

For all subjects randomized to a sham procedure, all activities will occur including I.V. lines, planning MRI's, etc, and an identical procedure will be performed with the energy output disabled. The treating physician will determine a sonication (treatment) time for sham subjects to be similar to that which is occurring in the treatment arm to maintain consistency between arms. It should be noted that all treatment times of study arms will be captured in the study CRF.

6.7 Follow-up

Subject follow-up will be completed at Day 1, Day 7, Month 1, and Month 3 for all subjects who underwent CL lesioning/ablation using ExAblate system. Subject follow-up will be similar for those who underwent sham treatment. At 3 months, subjects who had sham treatment will be unblinded and offered MRgFUS.

Subjects will be evaluated at all follow-up visits for general health, neurological changes and efficacy measurements as well as for device/procedure related adverse events that may have occurred during the follow-up period. Medication regimen and PRN usage will be recorded at each follow-up along with the following assessments:

6.7.1 Day 1

- Evaluation of general health and neurological changes
- NPRS (Worst pain in 24 hrs)
- PROMIS
- Assess patient blind
- Assess safety and update adverse events as needed
- Review medications and record any changes
- MRI

6.7.2 Day 7

- Evaluation of general health and neurological changes
- NPRS (Worst pain in 24 hrs)
- PROMIS
- PGIC
- Assess patient blind
- Assess safety and update adverse events as needed
- Review medications and record any changes
- MRI

6.7.3 Month 1

- Evaluation of general health and neurological changes
- NPRS (Worst pain in 24 hrs)
- PROMIS
- PGIC
- Assess patient blind
- Assess safety and update adverse events as needed
- Review medications and record any changes
- MRI

6.7.4 Month 3

- Evaluation of general health and neurological changes
- NPRS (Worst pain in 24 hrs)
- PROMIS
- PGIC
- Assess patient blind
- Neuropsychological Pain Assessment
- GAD-7
- PHQ-9
- PCS
- BBHI-2
- MRI

- Dynamic FDG PET
- Assess safety and update adverse events as needed
- Review medications and record any changes
- Evaluation by a pain management physician

All pre-treatment and post treatment MR images will be de-personified (i.e.: subject identifiers made anonymous), archived and sent to InSightec. These analyses will also include full radiological assessments from baseline through all follow up visits.

In this study, subjects who use alternative treatments (not including medication change) during the 3-month follow-up period will be exited from the study, after completing required study examinations. The reason(s) for study exit will be noted on the Case Report Forms.

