6.0 INVESTIGATIONAL PLAN

6.1 Study Design

This study is designed as a prospective, double-blinded, randomized trial in 10 subjects with sham procedures serving as the control. A rigorous clinical trial design is required for the subjective measurement of pain and clinical outcome where a placebo effect is anticipated. Primary safety and efficacy assessments will be made before and after treatment through the 3 month blinded phase. After 3 months, subjects in the sham arm will be offered a focused ultrasound bilateral thalamotomy as an open label extension of the study. All subjects receiving treatment, either during the primary blinded analysis or open-label extension phase, will be followed for at least 3 months post-thalamotomy.

Neuropathic Pain Study Flow

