9.8 Anticipated Treatment Side Effects from MRgFUS

All adverse events will be reported in the Case Report Forms (CRFs) and analyzed for their relation to the ExAblate device as well as other causes (Expected procedure findings, Drug/Contrast media reactions, Medical conditions, and Unrelated to device or procedure). Adverse events related to the device or procedure occur during or shortly after the procedure (within 30 days) since the effect is a one-time, focal treatment. Based on existing treatment experience in the brain using the ExAblate Neuro Type 1.0 (650 KHz), the following anticipated side effects have been identified as possibly occurring during/following the ExAblate procedure.

9.8.1 Procedure-related events include:

- Claustrophobia. Medications may be useful in controlling symptoms, but may also result in nausea/vomiting.
- Pain/discomfort:
 - Sonication-related headache or head/face flushing or warmth. Usually these are transient, but are coincident with a sonication. Headache may occasionally last for several days.
 - Headache may relate to the headframe or fasting status. The brain has no pain sensors, but the scalp, dura and bone tissues do.
 - Position-related pain related to being uncomfortable in the scanner (e.g., sore neck, back pain, muscle or joint pain).
- Hypertension/hypotension, and bradycardia/tachycardia may be related to pre-procedure nervousness or comorbid conditions / missed medication dose pre-procedure as an NPO requirement. Medications can be administered peri-procedure to control them.
- Neurological deficits may result from damage to nearby structures in the brain and thus is specifically related to the target location. To date, the following has been reported:
 - vestibular with or without vegetative manifestations
 - paresthesias
 - dysesthesias/pain.

9.8.2 Events which are Unrelated to the ExAblate device include:

- Events associated with the headframe, such as pin site pain, pin site or scalp/facial edema, pin site burning or bleeding.
- Events associated with the urinary catheter, such as urinary tract infection.

- Events associated with the intravenous line used to administer medications, such as infection and/or bruising.
- Events that are associated with comorbid conditions or unforeseen circumstances.

9.8.3 Drug reactions include:

- Nausea or vomiting
- Dizziness
- Overdose or mis-dosing in error

9.8.4 Events related to malfunction or mis-use of the device include:

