9.10 Criteria for Removal from the Study

Subjects can be exited from the study at any time if in the opinion of the principal investigator it is not in the best interest of the subject to carry on as planned. In addition, subjects may also choose to exit the study at any time, but will be strongly encouraged to participate in the follow-up visits for safety reasons (continued monitoring of subject safety).

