9.11 Criteria for Stopping the Study

The study will be stopped for evaluation should:

1. any death occur, or
2. if two or more subjects experience
 - a. a cerebrovascular hemorrhage
 - b. or serious related neurological adverse event
 - c. or a 50% increase in pain from Baseline following two consecutive visits starting from 7-days post treatment visit.

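### Section 6.7 exits users of non-medication alternative treatments without defining which examinations come first, so remaining Month 1 and Month 3 data after a one-time procedure may be lost

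*Protocol*

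**What the plan says.** - **The exit rule.** The last paragraph of section 6.7 says that "subjects who use alternative treatments (not including medication change) during the 3-month follow-up period will be exited from the study", and the sentence ends "after completing required study examinations". The reason for exit goes on the case report form. Medication changes are excepted here; section 8.2 deals with them separately.
- **The follow-up commitments.** Section 6.7 opens with "Subject follow-up will be completed at Day 1, Day 7, Month 1, and Month 3 for all subjects who underwent CL lesioning/ablation" and calls sham follow-up similar. Section 6.1 says that all subjects who receive the treatment "will be followed for at least 3 months post-thalamotomy". Section 6.2 follows sham subjects for 3 months.
- **The other exit route.** Section 9.10 begins "Subjects can be exited from the study at any time if in the opinion of the principal investigator" and goes on to the subject's best interest. Its encouragement to keep attending visits is worded for subjects who choose to leave. It is silent on follow-up after removal by the investigator.
- **Safety reporting.** Section 3.1 makes worsening pain part of the safety analysis. Section 10.0 says that progression leading to an alternative treatment is not reported as an adverse event.
- **The stopping criterion.** Section 9.11(2)(c) applies "if two or more subjects experience" the following: "a 50% increase in pain from Baseline following two consecutive visits starting from 7-days post treatment visit".

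**The concern.** The procedure is given once. Section 9.8 explains the timing of related adverse events with the words "since the effect is a one-time, focal treatment". Exiting a subject afterwards therefore cannot withdraw exposure; it can only end observation.

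The trigger arises after randomisation and probably reflects unrelieved pain. The population makes it a realistic event, because section 5.2 requires failure of at least three medications and at least one interventional therapy.

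Two things are at stake. The 3-month change in worst NPRS could be missing for the subjects who did worst, and unequally between arms. Safety, which section 3.2 names as the primary outcome and bases on adverse events and MRI, could also lose its later visits. For an exited subject whose pain worsened, section 10.0 keeps the progression out of the adverse-event record. The reason for exit might then be the only trace.

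**Working it through.** The protocol gives no power calculation, no exit rate and no standard deviation, and section 8.4 proposes no statistical analysis. There is no planned figure to reproduce. The check sets the passages side by side and then sizes one exit.

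**1. Two readings of the undefined term**

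| Reading of the required examinations | Data after exit | Consequence |
|---|---|---|
| An exit visit | Remaining Month 1 and Month 3 NPRS, PROMIS, PGIC, MRI and adverse events, and the Month 3 PET, are not collected | Contradicts 6.1 and the opening of 6.7, and 6.2 for sham subjects |
| All visits through Month 3 | Nothing is lost | The exit has no data function. It is unclear whether an exited sham subject keeps the offer made in 6.1, 6.2, 6.4 and 6.7 |

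Nothing elsewhere settles the choice. Section 8.1 keeps anyone with at least one sonication in the safety set, but membership of a set does not schedule a visit.

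**2. Size of one exit**

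Inputs: 10 subjects randomised 1:1 (8.4), so about 10 / 2 = 5 per arm. A mean change of 2 points is described as clinically significant (8.2). The individual changes below are assumptions.

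- Share of an arm: 1 / 5 = 20%.
- Let the four remaining subjects improve by a mean m and the exited subject by x. The full-arm mean is (4m + x) / 5; the mean seen without that subject is m.
- m = 2.0, x = 0: (8 + 0) / 5 = 1.6, against 2.0 observed. Difference 0.4.
- m = 2.0, x = −3 (pain 3 points worse): (8 − 3) / 5 = 1.0, against 2.0 observed. Difference 1.0.
- With no assumption about x, a missing Month 3 score can lie anywhere from 0 to 10. The arm mean is then undetermined over a width of 10 / 5 = 2.0 points, the same as the 2-point change in 8.2.

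**3. Effect on criterion 9.11(2)(c)**

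The visits from Day 7 are Day 7, Month 1 and Month 3, which give two consecutive pairs.

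- No visit after Day 7: 0 of 2 pairs remain.
- No visit after Month 1: 1 of 2 pairs remains.
- All visits kept: 2 of 2 pairs remain.

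The criterion does not name its pain measure. If it is the 0 to 10 NPRS, a 50% rise means 1.5 × baseline: 7.5 from 5, 9.0 from 6, and 10.5 from 7, which is off the scale. With entry at a worst score of 5 or more (5.2), only subjects with a baseline of 5 or 6 can meet it, whether or not anyone is exited.

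**The case against.** The strongest reply is that the text can be read harmoniously. Section 6.7 opens with follow-up through Month 3 for all lesioned subjects, and the visit table stands under a heading about study requirements (section 7.0). If the required examinations are that schedule, nothing is lost and 6.1 is respected. This is a fair reading, and it is why data loss cannot be called certain. The wording does not establish it, though, and the ordinary sense of being exited points the other way.

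A second reply is that the study is small and descriptive, and that missing scores belong in the statistical analysis plan. That holds for denominators and for how missing values are displayed. It does not answer the main point, because an analysis plan cannot recover visits that the protocol has ended.

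A reader might infer several stronger things that the documents do not support:

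- **That exited subjects are dropped from the efficacy analysis.** Section 6.7 does not say so. The exclusion stated in 8.2 concerns medication change.
- **That one exit could both lift a 1.6-point mean to 2.0 and turn four responders of five into four of four.** A responder in 8.2 improves by at least 3 points. Four responders imply m of at least 3.0 and a full-arm mean of at least 0.8 × 3.0 = 2.4 if the fifth does not change, so the two cannot occur together.
- **That the exit rule defeats the stopping criterion.** The effect is narrow: an exit visit might count as the second visit, two subjects are needed, and on the NPRS only baselines of 5 or 6 can qualify.
- **That 9.10 rules out follow-up after investigator removal, or that 6.7 bars sham subjects from crossover.** The first is silence and the second is unclear; neither is stated.

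**Conclusion.** The point holds as an undefined term with a harmful plain reading. Under the exit-visit reading, section 6.7 conflicts with 6.1 and with its own opening, and it ends observation of subjects selected by a probable treatment failure. Neither 8.1 nor 9.10 repairs this, and 10.0 removes one other place where worsening pain would appear. Under the Month 3 reading no data are lost, but the exit then does nothing except cloud the crossover offer. Either way the passages must be reconciled.

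One exit is 20% of an arm of 5. In the illustration it makes the arm mean look 0.4 points better (exited subject unchanged) to 1.0 points better (exited subject 3 points worse), given a mean improvement of 2.0 in the other four. These changes are assumptions. The protocol gives no exit rate, and the direction of the bias in the between-arm difference depends on which arm loses subjects.

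The effect on 9.11(2)(c) is secondary and calls for clarification only. The amendment is worth making because it is cheap and protects the primary safety data and the 3-month NPRS comparison.

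**What to change.** Replace the exit sentence in 6.7 with text such as: *Subjects who use a non-medication alternative treatment, or whom the investigator removes under 9.10, remain in the scheduled follow-up through Month 3 unless they withdraw consent. NPRS, PROMIS, PGIC and adverse events are collected at each visit, with MRI and PET where not contraindicated. The type and date of the alternative treatment are recorded, and Month 3 scores obtained after it are flagged.*

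Then:

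- Reconcile 6.7 with 6.1, 9.10 and 10.0, including how worsening pain that leads to another treatment is captured, given 3.1.
- Have the sponsor state how such subjects are counted under 9.11(2)(c). This asks for clarification of the existing criterion, not a new stopping rule.
- State whether sham subjects who use an alternative treatment keep the crossover offer.

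The cost is a short amendment. The visits are already scheduled, so no visit or procedure is added. The downside is that some Month 3 scores will be taken after another treatment, which is why they need a flag. MRI may not be possible for a subject who has received an incompatible implant.

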7.0 STUDY REQUIREMENTS AND VISIT SCHEDULE

The table below summarizes the study visit schedule and procedures.

Procedures	Screening	Baseline (within 1 week of day 0)	Day 0 (Proced- ure)	Day 1	Day 7 (±3 days)	Months 1 (±7 days)	Month 3 (±14 days) ¹
Written Consent	X						
Check Eligibility	X						
Demographics	X						
History and Physical Exam		X					
Screening Labs	X						
CT Scan	X						
MRI	X			X	X	X	X
Dynamic PET		X					X
NPRS and PROMIS Pain Questionnaires ²	X	X		X	X	X	X
PGIC					X	X	X
Neurological Exam	X			X	X	X	X
Pain Psychological Exam ³	X						X
Pain Management Exam	X						X
MRgFUS Treatment or Sham Procedure			X				
Assessment of patient blind			X	X	X	X	X
Concomitant Medications (prescribed and PRN)	X	X	X	X	X	X	X
Adverse Events			X	X	X	X	X

¹ Subjects will be un-blinded to randomization arm at the completion of month 3 visit. Subjects who initially were randomized to the sham arm may go back to day 0 in schedule of events and receive an unblinded MRgFUS thalamotomy.

² Five PROMIS fixed length short forms to be completed on paper at each indicated timepoint. PROMIS scale v1.0: Pain Intensity 3a, Pain Behavior 7a, Pain Interference 8a. PROMIS scale v2.0: Neuropathic Pain Quality 5a, Nociceptive Pain Quality 5a.

³ To include: GAD-7, PHQ-9, PCS, BBHI-2

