10. Severe hypertension (diastolic BP > 100 on medication)

11. Subjects with standard contraindications for MR imaging such as non-MRI compatible implanted metallic devices including cardiac pacemakers, size limitations, etc.

12. On medications that increase the bleeding risk, we are following the published guidelines which are currently recognized by the American Society of Regional Anesthesia and Pain Medicine, American Academy of Pain Medicine and the North American Neuromodulation Society (Reg Anesth Pain Med 2015;40: 182–212); specifically:

- a. Aspirin or another antiplatelet medication (clopidogrel, prasugrel, ticlopidine, abciximab) for the last 7 days prior to treatment.
- b. Oral, subcutaneous or intravenous anticoagulant medications, such as oral vitamin K inhibitors for the last 7 days, non-vitamin K inhibitor oral anticoagulant (dabigatran, apixaban, rivaroxaban) for the last 72 hours.
- c. Intravenous or subcutaneous heparin-derived compounds for the last 48 hours.

13. Individuals who are not able or willing to tolerate the required prolonged stationary supine position during treatment (can be up to 4 hours of total table time.)

14. Subjects participating or have participated in another clinical trial in the last 30 days

15. Presence of systemic neurological disease or dysfunction

16. Known life-threatening systemic disease

17. Subjects with risk factors for intraoperative or postoperative bleeding from a documented coagulopathy or if their serum coagulation studies (platelet count, PT, PTT, and INR) exceed the institutional laboratory limits.

18. Subjects with brain tumors or any significant intracranial mass. *Trigeminal or cavernous sinus tumors causing neuropathic pain are not excluded.*

19. Any illness that in the investigator's opinion preclude participation in this study

20. Pregnancy or lactation

21. Legal incapacity or limited legal capacity

22. Subjects with a deep brain stimulation implant or with a prior stereotactic thalamic ablation

23. Skull density ratio, calculated from the baseline noncontrasted head CT, is less than 0.4

24. History of hemorrhagic stroke or cerebrovascular event within the past year of treatment exhibiting incomplete resolution

25. History of seizures within past year of treatment

26. Severe kidney disease or on dialysis

[figure not shown]
27. Subjects who are unable to tolerate medications due to intolerable side effects.

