6.2 Sham Study Design

The randomized, control arm subjects will undergo a sham procedure that is identical to the treatment except the energy output will be disabled. These control subjects will then be followed up for 3-months post-sham procedure to assess study endpoints; study follow-up: 1 day, 1 week, 1 and 3 month visits.

At the 3-Month time point, all subjects will be unblinded and offered crossover to the actual treatment. All these crossover subjects will be followed again according to the same schedule as the treatment through the Month 3 post treatment study visit.

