6.3 Pre-Treatment Procedures

1. PRE-SCREENING: Subjects with medication-refractory, trigeminal or other craniofacial neuropathic pains may be eligible for the study. The diagnosis will be confirmed by the neurosurgeon from the patient's medical history and physical examination.
2. CONSENT: Those who meet the preliminary criteria for the study based on pre-screening of available information will be offered an Informed Consent to sign prior to further evaluation (see Appendix-B for an Informed Consent template). Those who accept will be assigned a subject study number. No study specific tests or procedures will be done until the subject has signed consent.
3. SCREENING and ENROLLMENT:
 - a. All current medications will be documented in the medical record and any changes over the past two months will be noted. Record prescribed and PRN medication usage.
 - b. The investigator will review and document any medical history that pertains to study eligibility.
 - c. Subjects will complete screening questionnaires
 - Worst 24 Hr NPRS assessment, including report of pain levels over past two months (for eligibility)
 - PROMIS (patient reported outcomes of pain)
 - a. Intensity
 - b. Neuropathic pain quality
 - c. Nocioceptive pain quality
 - d. Behavior
 - e. Interference
 - d. Focused neuro-exam by neurosurgeon including:
 - Cranial nerve examination
 - Sensory examination
 - Gait
 - e. Screening blood tests: Blood will be drawn by venipuncture for PT, PTT, Metabolic panel, and CBC including platelets
 - f. Women of childbearing age will undergo a urinary or serum Beta-hCG test for pregnancy. If the test is positive, the subject will be excluded from the study. If the test is negative, she must agree to maintain a suitable form of birth control throughout study. This includes the screening period until study completion.

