6.5 Treatment Procedures

On the day of the treatment, the following clinical team members should be present:

Neurosurgeon: leads the planning and guidance of the treatment. They will also monitor the neurological performance and clinical status of the subject. They will be responsible for the overall management of the subject. The neurosurgeon will evaluate the subject's comfort level and direct sufficient sedation to maintain this comfort. Feedback of symptom relief is not expected to be necessary for this procedure.

The anesthesiologist or nurse anesthetist: they will monitor vital signs and provide necessary medications to keep the subject comfortable.

The overall treatment procedure steps will be performed as follows:

1. Subjects will be reminded to not take any anticoagulant (e.g. warfarin) or antiplatelet (e.g. aspirin) therapy in the week prior to and in the week after the focused ultrasound procedure.
2. The subject will be instructed not to eat or drink after midnight prior to the MRgFUS procedure, in order to permit the use of immediate general anesthesia in case of a treatment complication that may require emergency intervention.
-
3. Medications will be reviewed to confirm regimen is unchanged since study enrollment. Record prescribed and PRN medication usage.
4. An IV line will be positioned for the delivery of fluids and any medications required during the procedure. Some of the subjects may require a urinary catheter to keep the bladder empty during treatment. Noninvasive monitoring of heart rate, blood pressure, systemic oxygen saturation, electrocardiogram, and end-tidal CO₂ will be maintained throughout the procedure using standard MR-compatible monitoring devices.
 - The anesthesiologist or nurse anesthetist will administer appropriate medications for subject management if necessary. Since the medial thalamotomy procedure is image-guided and does not rely on intraprocedural feedback for targeting, intravenous sedation may be used as necessary for comfort. Subjects will not be intubated.
5. The subject's head will be carefully shaved and examined for pre-existing scalp scars or any other scalp lesions.
6. Graduated compression stockings will be worn to prevent deep venous thrombosis in the lower limbs.
7. The subject's head will be placed in the immobilization unit (similar to those used in stereotactic radiotherapy head fixation).
8. Subject will be positioned supine and headfirst on the MRgFUS therapy table.

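### Sham subjects who cross over re-enter at Day 0, so no repeat eligibility check, clotting tests or pregnancy test is required before their first real ablation

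*Protocol*

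**What the plan says.** After the Month 3 visit and unblinding, a sham subject "may go back to day 0 in schedule of events and receive an unblinded MRgFUS thalamotomy" (section 7.0, footnote 1). Section 6.2 adds: "All these crossover subjects will be followed again according to the same schedule as the treatment through the Month 3 post treatment study visit".

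In the section 7.0 table, the rows for the eligibility check and the screening laboratory tests each carry a single mark, under Screening. Section 6.3 places the blood draw (PT, PTT, metabolic panel, blood count with platelets) in item 3e. Item 3f reads: "Women of childbearing age will undergo a urinary or serum Beta-hCG test for pregnancy". The principal investigator's eligibility sign-off is item 3k. All three are screening steps.

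Two exclusions in section 5.3 depend on these results. Item 17 excludes subjects with a documented coagulopathy or whose "serum coagulation studies (platelet count, PT, PTT, and INR) exceed the institutional laboratory limits". Item 20 excludes pregnancy and lactation. Section 9.5 lists hemorrhage among the primary risks of the procedure and relies on excluding coagulopathy as part of its mitigation.

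**The concern.** The sham delivers no energy (section 6.5), so the crossover procedure is the subject's first real lesion, and it is permanent and bilateral. The protocol's protection against bleeding and against treating a pregnant subject rests partly on tests taken before the sham procedure. Footnote 1 takes the subject past the only column in which those tests and the eligibility decision appear. A site that follows the schedule exactly could therefore ablate on results several months old. A clotting disorder, a fall in platelets or a pregnancy arising in the meantime would not have to be looked for. The stake is the safety of the open-label crossover subjects.

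**Working it through.** The protocol gives no figure to reproduce here. The check is a comparison of the places where a repeat test could be required, followed by one short calculation.

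**Where a repeat could be required**

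- Day 0 column, section 7.0: the procedure, the blinding question, medications and adverse events. No laboratory tests, pregnancy test or eligibility check.
- Treatment steps, section 6.5: an anticoagulant and antiplatelet reminder and a medication review. No laboratory tests or pregnancy test.
- Month 3 visit, section 6.7.4: health and neurological evaluation, pain scales, psychological and pain-physician assessments, MRI and PET. No laboratory tests, pregnancy test or eligibility review.
- Section 6.2: repeats the follow-up schedule and does not mention screening.
- Study flow figure, section 6.1: not visible in the text available, so it could not be checked.

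**Age of the tests at crossover**

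Inputs: the Month 3 visit has a window of ±14 days (section 7.0). Month 3 is taken as 90 days (assumption). Let *a* be the interval from screening to the sham procedure and *b* the interval from the Month 3 visit to the crossover procedure. The protocol caps neither.

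Age of tests = *a* + (90 ± 14) + *b*

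- Earliest Month 3 visit: 90 − 14 = 76 days; 76 / 7 = 10.9, about 11 weeks.
- Latest Month 3 visit: 90 + 14 = 104 days; 104 / 7 = 14.9, about 15 weeks.

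With *a* and *b* both at zero, the tests are at least about 76 days old. Any positive *a* or *b* adds to that. For a directly treated subject the age is simply *a*, so crossover adds at least 76 days.

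**Number of subjects**

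Ten subjects are randomised 1:1 (section 8.4), so 10 × 1/2 = 5 are expected in the sham arm. About 5 are exposed if all accept crossover.

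**What the remaining safeguards test**

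- Contraception agreement, section 6.3 item 3f ("This includes the screening period until study completion"): lowers the chance of pregnancy but does not detect one.
- Exclusion 12a, which bars antiplatelet drugs "for the last 7 days prior to treatment", and the section 6.5 reminder: address drug-related bleeding only.
- Section 6.5 item 3: "Medications will be reviewed to confirm regimen is unchanged since study enrollment". This reviews drugs, not clotting or platelets.
- Month 3 visit, section 6.7.4: "Evaluation of general health and neurological changes". This is a clinical assessment without bloods.
- DVT screening, section 9.3: addresses thrombosis, not bleeding tendency.

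None of these measures clotting or platelets, and none tests for pregnancy.

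**The case against.** Four counter-arguments carry weight.

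*The interval is probably short.* Section 6.4 offers crossover at the end of the three-month visit, section 6.2 offers it at the 3-month point, and section 4.1 describes three blinded months followed by a further three open-label months. A reader might infer from the missing cap that crossover could come at any later time. The text does not support that as the intended conduct, because it points to crossover soon after Month 3. But even with no delay at all, the tests are at least about 76 days old.

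*The gap is not confined to crossover.* No maximum test age is stated for directly treated subjects either. A reader might see a defect of the crossover path alone. In fact the general omission is a test-validity window, and footnote 1 adds roughly 11 weeks or more to it.

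*Crossover subjects are not unassessed.* Exclusions 24 and 25 are also timed to treatment. Section 6.3 item 3l schedules an anesthesiology evaluation, though footnote 1 does not repeat it, and section 9.10 lets the investigator withdraw a subject at any time. A site may also repeat bloods as usual practice. This narrows the point to specific missing tests and a missing eligibility re-confirmation; it does not supply them.

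*The baseline is not really undefined.* Because footnote 1 also skips the Baseline column, a reader might infer that the pain-worsening stopping rule (section 9.11, item 2c) has no usable reference for crossovers. Sections 6.3 and 7.0 tie Baseline to the week before the procedure, which favours the pre-ablation value, and Month 3 scores are collected anyway. The rule also needs two or more subjects, and any shift in its threshold depends on a fall in pain during the sham phase that the protocol does not give. That leaves a clarification only.

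**Conclusion.** The point holds as a safety gap in the schedule. As written, about 5 of 10 subjects could have their first actual ablation without a current eligibility check, clotting tests, platelet count or pregnancy test, on results at least about 76 days old and with no explicit maximum. This rests on taking Month 3 as 90 days, on all sham subjects accepting crossover, and on the unseen flow figure adding no re-screening step.

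The residual risk cannot be sized, because the protocol gives no rate at which coagulopathy, thrombocytopenia or pregnancy would arise over this interval. A reader might also infer that the trial's efficacy result is compromised. It is not: crossover follows the Month 3 visit, so the randomised comparison is complete by then. The change is worth making because it is cheap and precedes an irreversible procedure.

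**What to change.** Amend footnote 1 to require, within a stated window before the crossover procedure, re-confirmation of eligibility, PT, PTT, INR and platelets and, where applicable, a beta-hCG test. One week would match the protocol's existing Baseline window. Preferably, state the same maximum test age before any procedure in either arm.

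As an optional clarification, name the pre-ablation value as the crossover baseline: the sham Month 3 assessment or, if the gap is long, NPRS and PROMIS repeated within 1 week of the procedure. Using the Month 3 PET for this purpose avoids a further scan of about 10 mSv (section 9.1).

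The cost is one reworded footnote plus routine bloods and, where applicable, a pregnancy test in about five subjects. Some subjects may be found ineligible at that point, which is the purpose of the check.
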